9.2.1.4 Definition of Virologically-confirmed COVID-19 Case

For the randomized observer-blinded phase, a virologically-confirmed case of COVID-19 is defined as a positive SARS-CoV-2 specific RT-PCR test in a person with clinically symptomatic disease consisting of 1 or more of the following symptoms (based on the same screening symptoms as above):

- Fever or chills
- Shortness of breath or difficulty breathing
- New loss of taste or smell
- o Cough
- o Fatigue

- $\circ~$ Muscle or body aches
- o Headache
- Sore throat
- Congestion or runny nose
 - o Nausea or vomiting
 - o Diarrhea

This definition is intended to capture all severities of virologically-confirmed clinically symptomatic cases of COVID-19. As such, COVID-19 cases classified by severity (e.g., mild or severe) will be a subset of these cases. See Appendix 3 and Appendix 4 for clinical definitions of severe and mild COVID-19, respectively.

For the open-label phase, virologically-confirmed case of COVID-19 is defined as a positive SARS-CoV-2 specific RT-PCR test in a person with clinically symptomatic disease.

9.2.1.5 COVID-19 Case Definition for Primary Efficacy Analysis (Randomized Observer-blinded Phase only)

For the primary analysis of efficacy, the case must meet the following criteria:

- Must be a virologically-confirmed case of COVID-19 (of any severity) defined as a positive SARS-CoV-2 specific RT-PCR test in a person with clinically symptomatic COVID-19, as defined above in Section 9.2.1.4.
- Symptom onset must have occurred \geq 15 days following the second trial vaccination.
- The subject must not have a history of virologically-confirmed COVID-19 illness at enrollment or have developed a case of virologically-confirmed COVID-19 before 15 days following the second trial vaccination (see Section 10.2.3, Efficacy Analysis Set [EAS] for more details).
- The subject must have been SARS-CoV-2 naïve at baseline and Day 43 (defined as seronegative to N protein in the blood samples collected at baseline and Day 43).

The primary efficacy cases must be confirmed by the Adjudication Committee.

Day 43 is 14 days post-second dose which allows the immune response to CVnCoV to mature and reach its height following the second dose. As such, COVID-19 case ascertainment starting the next day at \geq 15 days represents the evaluation of full VE of CVnCoV against COVID-19.

9.2.1.6 SARS-CoV-2 Genome Lineage Characterization (Randomized Observer-blinded Phase only)

The characterization of SARS-CoV-2 variants in this trial will be implemented by viral whole genome sequencing of nasopharyngeal swab samples of subjects followed by

Clinical Trial Protocol	CV-NCOV-004
CureVac AG	COVID-19 mRNA Vaccine

comparison with previously sequenced and typified genomes. Analysis will follow the methodology to assign names to lineages of SARS-CoV-2 using a dynamic nomenclature [34], using the software pangolin (V2) (https://cov-lineages.org/). The assignment algorithm uses machine learning, which offers a classification tree that has been trained using over approximately 60,000 SARS-CoV-2 sequences retrieved from GISAID, machine learning reconstruction and manual curation for all the lineages. Each base per genome was one-hot encoded, which makes every position informative for further prediction. Those models are available under cov-lineages/pangoLEARN at github (https://github.com/cov-lineages/pangoLEARN/tree/master/pangoLEARN).

The characterization will be done centrally. The following phylogenetic clustering will be applied:

- 1. "Wild type" virus: WT/D614G, lineages A.1/B.1 without the VOCs (i.e., without B.1.1.7 [Alpha], B.1.351 [Beta], B.1.429 [Epsilon])
- 2. "UK" VOC: B.1.1.7 (Alpha)
- 3. All other variants of concern.

In this trial, the primary efficacy endpoint will be based on all strains, the "wild type" virus and all SARS-CoV-2 variants (as defined under numbers 1, 2, and 3 above); the key secondary efficacy endpoint will be based on the "wild type" virus and the UK variant B.1.1.7 (Alpha) (as defined under numbers 1 and 2 above); and the exploratory efficacy endpoint will be based on disease caused by individual variants of concern (as defined under numbers 2 and 3 above).

9.2.1.7 Adjudication of COVID-19 Cases (Randomized Observer-blinded Phase only)

An independent Committee of clinicians will be formed to adjudicate COVID-19 cases. The Committee will be blinded to the treatment assignment of the subject. The cases will be adjudicated by the members with respect to the following questions consistent with the endpoints of the trial.

- Is the case a virologically-confirmed case of COVID-19 defined as a positive SARS-CoV-2 specific RT-PCR test in a person with clinically symptomatic COVID-19 with 1 or more of the symptoms listed above in Section 9.2.1.4.
 - Was the RT-PCR test performed at the CureVac designated central laboratory?
- Was the symptom onset of the case ≥ 15 days following the second vaccination? Or did it occur before 15 days following the second trial vaccination?
- Was the subject naïve or non-naïve to SARS-CoV-2 at baseline and Day 43? (defined as being seronegative or seropositive to the SARS-CoV-2 N protein).
- Was the subject 18 to 60 years of age or ≥ 61 years of age?
- Was the subject asymptomatic? If asymptomatic, was the RT-PCR test positive ≥ 15 days following the second vaccination or before?
- Was it a mild or severe case of COVID-19 based on the provided clinical definitions?

Clinical Trial Protocol	CV-NCOV-004
CureVac AG	COVID-19 mRNA Vaccine

- Did the subject require supplemental oxygenation? What type of oxygen support did the subject receive?
- Was the subject hospitalized? Was the subject admitted to the intensive care unit?
- Did the subject die? Due to COVID-19 or other cause?

9.2.2 Asymptomatic Cases of SARS-CoV-2 Infection (Randomized Observer-blinded Phase only)

There will be no active surveillance in this trial for asymptomatic SARS-CoV-2 infections. Subjects will be reminded to contact the site immediately if he/she had a positive SARS-CoV-2 test performed outside of the site, whether they were symptomatic (COVID-19 illness) or asymptomatic at the time of the test. Subjects without symptoms may have been tested for several reasons, for example, close exposure to a known person with SARS-CoV-2 infection or as part of their routine screening as a healthcare provider.

If the subject was asymptomatic, trial staff will contact the subject immediately to collect information about the positive SARS-CoV-2 test the subject reported. The subject should be retested as soon as feasible to confirm the result. A nasopharyngeal swab sample should be sent to the Sponsor-designated central laboratory for RT-PCR testing; a positive RT-PCR test result will be considered definitive as a virologically-confirmed case of SARS-CoV-2 infection.

If the subject is confirmed to have SARS-CoV-2 infection, the subject will be followed by trial staff for at least 2 weeks for the development of any COVID-19 symptoms, to ensure that this is an asymptomatic infection. If the subject develops COVID-19, he/she will be followed-up as a COVID-19 case. If the subject is confirmed to be asymptomatic, information will be collected by the trial staff and documented on the appropriate eCRF page.

If the subject is not virologically-confirmed by RT-PCR testing, he/she will return to routine surveillance for COVID-19 as a subject who is naïve to SARS-CoV-2 infection (unless determined otherwise by a seropositive test to the N protein).

9.3 Safety Assessments

9.3.1 Safety Assessments for Subjects in the Randomized Observer-blinded Phase

The safety and reactogenicity of a 2-dose schedule of CVnCoV will be assessed as described below.

9.3.1.1 Safety Assessments Specific for Subjects in Phase 2b

- Reactogenicity will be assessed daily on each vaccination day and the following 7 days by collection of solicited local AEs (injection site pain, redness, swelling, and itching) and systemic AEs (fever, headache, fatigue, chills, myalgia, arthralgia, nausea/vomiting, and diarrhea) using eDiaries. In addition, other indicators of safety will be collected (e.g., body temperature).
- The eDiary will also be used as a memory aid for the subject for the collection of unsolicited AEs on each vaccination day and the following 28 days.

Clinical Trial Protocol	CV-NCOV-004
CureVac AG	COVID-19 mRNA Vaccine

9.3.1.2 Safety Assessments for All Subjects in Phase 2b and Phase 3

- Medically-attended AEs will be collected through 6 months after the second trial vaccination.
- AESIs will be collected throughout the trial. AESIs to be monitored include pIMDs, AESIs for SARS-CoV-2 vaccines, and non-serious intercurrent medical conditions that may affect the immune response to vaccination.
- SAEs will be collected throughout the trial.
- AEs leading to vaccine withdrawal or trial discontinuation will be collected throughout the trial.

{If the subject does not receive their second trial vaccination, the AE follow-up time (6 months) will be determined based on the date scheduled for their second vaccination on Day 29}.

9.3.2 Safety Assessments for Subjects in the Open-label Phase

- AESIs will be collected until EOT (Day 393 of the original Phase 2b/3 schedule). AESIs to be monitored include pIMDs and AESIs for SARS-CoV-2 vaccines.
- SAEs will be collected until EOT (Day 393 of the original Phase 2b/3 schedule).
- AEs leading to trial discontinuation will be collected until EOT (Day 393 of the original Phase 2b/3 schedule).

9.3.3 Adverse Events

Definitions of AEs/SAEs, procedures for recording, evaluating, follow-up and reporting of AEs/SAEs/pregnancy/overdose, as well as assessments of intensity and causality of AEs, are provided in Appendix 10.

In Phase 2b, any AEs occurring during the 30-minute observation period after vaccination will be recorded in the eCRF. In Phase 3, only those AEs occurring during the 30-minute observation period after vaccination which constitute an AESI, medically-attended AE, or an SAE will be recorded in the eCRF.

It is important to note that COVID-19 illness and its complications/sequelae are consistent with the efficacy endpoints of the trial and, as such, should not be recorded as AEs. These data will be captured on the relevant eCRF pages for cases of COVID-19 illness that occur in the trial, which are expected outcomes of the trial. Only for any complications and sequelae of COVID-19 illness not mentioned on the COVID-19 summary form in the eCRF, an AE form needs to be completed. For consistency, the reporting procedure for COVID-19 cases in the open-label phase will remain as in the randomized observer-blinded phase despite the efficacy analysis is already completed. COVID-19 illness and its complications/sequelae as well as all symptoms listed in Section 9.2.1.4 will not be reported according to the standard expedited process for SAEs, even though the event may meet the criteria for an SAE. However please note that all fatal cases resulting from COVID-19 and its complications/sequelae and from all other events will be reported as SAEs and need to be reported to the CRO within 24 hours (see section Reporting of SAEs in Appendix 10).

Clinical Trial Protocol	CV-NCOV-004
CureVac AG	COVID-19 mRNA Vaccine

The reporting period for each type of AE and corresponding concomitant medication use is shown in Table 6.

АЕ Туре	Days 1 to 8	Days 29 to 36	Days 1 to 57	Day 1 to Month 6 ^a	Day 1 to EOT
Solicited AEs (Phase 2b)	Х	Х			
Unsolicited AEs (Phase 2b)			X		
Medically-attended AEs				Х	
SAE/AESI/COVID-19 fatal cases					Х
Any vaccination other than CVnCoV					Х
Any immune-suppressive/ modulating medication or other prohibited medication					Х
Non-serious intercurrent medical conditions that may affect the immune response to vaccination					Х

 Table 6
 Reporting Period by Type of Adverse Event

AE; adverse event; AESI: AE of special interest; AV: Authorized/licensed vaccines for preventing COVID-19; EOT: End of Trial; SAE: serious AE.

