5.5 Stopping/Pausing Rules for Safety

5.5.1 Individual Subject Stopping Rules

The individual subject stopping rules are met in case any of the following events occur after the first trial vaccination:

- An allergic/anaphylactic reaction considered as related to the trial vaccine
- Any SAE considered as related to the trial vaccine

If any of these rules are met, the subject must not receive the second vaccine dose. The subject will be encouraged to continue participation until the end of the trial for safety.

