9.3.3.1 Solicited Adverse Events

An eDiary will be distributed to all subjects in Phase 2b for collection of solicited local AEs (injection-site pain, redness, swelling and itching) and solicited systemic AEs (fever, headache, fatigue, chills, myalgia, arthralgia, nausea/vomiting and diarrhea) on the day of vaccination and the following 7 days. Subjects will be given a thermometer to measure body temperature orally and a measuring tape to determine the size of local injection site reactions. Subjects will be instructed on how to enter the solicited AEs daily for 7 days in the eDiary.

Solicited AEs will be assessed on an intensity scale of absent, mild, moderate and severe (Table 7 and Table 8). By definition, all local solicited AEs are considered related to trial vaccination. For solicited systemic AEs, the Investigator will assess the relationship between trial vaccine and occurrence of each AE and make an assessment of intensity for each AE.

If concerning to the subject or of prolonged duration, solicited Grade 3 AEs should be reported to the Investigator immediately. In case of related Grade 3 solicited AEs reported for more than 1 day on the eDiary, the subject will be questioned to establish the total duration of the AE as exactly as possible.

Table 7 Intensity Grading* for Solicited Local Adverse Events

Adverse Event	Grade/Intensity	Definition
Pain at	0	Absent
Injection	1	Does not interfere with activity
Site	2	Interferes with activity and/or repeated use of non-narcotic pain reliever > 24 hours
	3	Prevents daily activity and/or repeated use of narcotic pain reliever
Redness	0	< 2.5 cm
	1	2.5 – 5 cm
	2	5.1 – 10 cm
	3	> 10 cm
Swelling	0	< 2.5 cm
	1	2.5 – 5 cm and does not interfere with activity
	2	5.1 – 10 cm or interferes with activity
	3	> 10 cm or prevents daily activity
Itching	0	Absent
	1	Mild, no interference with normal activity
	2	Moderate, some interference with normal activity
	3	Significant, prevents normal activity

*FDA toxicity grading scale [35].

Table 8	Intensity Grading* for Solicited Systemic Adverse Events
	intenetty enduring for concited eyetenne Autoroc Erente

Adverse Event	Grade/Intensity	Definition
Fever	0	< 38°C
	1	≥ 38.0 – 38.4°C
	2	≥ 38.5 – 38.9°C
	3	≥ 39°C
Headache	0	Absent
	1	Mild, no interference with normal activity
	2	Moderate, some interference with normal activity and/or repeated use of non-narcotic pain reliever > 24 hours
	3	Significant; any use of narcotic pain reliever and/or prevents daily activity

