Appendix 9 Adverse Events of Special Interest (AESIs) for SARS-CoV-2 Vaccines

Current list of AESIs {based on Brighton Collaboration via CEPI's Safety Platform for Emergency vACcines (SPEAC) Project}:

Immunological disorders:

Clinical Trial Protocol

CureVac AG

- o Anaphylaxis
- o Vasculitides
- o Enhanced disease following immunization
- o Multisystem inflammatory syndrome in children (MIS) and adults

Respiratory disorders:

o Acute Respiratory Distress Syndrome

Cardiac disorders:

- Acute cardiac injury including:
 - o Microangiopathy
 - o Heart failure and cardiogenic shock
 - o Stress cardiomyopathy
 - o Coronary artery disease
 - o Arrhythmia
 - o Myocarditis, pericarditis

Hematological disorders:

o Thrombocytopenia

Coagulation disorder:

- o Deep vein thrombosis
- o Pulmonary embolus
- o Cerebrovascular stroke
- o Limb ischemia
- o Hemorrhagic disease

Renal disorders:

o Acute kidney injury

Gastrointestinal disorders

- o Liver injury
- o Acute pancreatitis

Neurological disorders:

- o Generalized convulsion
- o Guillain-Barré Syndrome
- o Acute disseminated encephalomyelitis
- o Anosmia, ageusia
- o Meningoencephalitis

Dermatologic disorder:

- o Chilblain-like lesions
- o Single organ cutaneous vasculitis
- o Erythema multiforme

Other:

o Serious local/systemic AR following immunization

Appendix 10 Adverse Events: Definitions and Procedures for Recording, Evaluating, Follow-up, and Reporting

It is important to note that COVID-19 and its complications/sequelae are consistent with the efficacy endpoints of the trial and, as such, should not be recorded as AEs. These data will be captured on the relevant eCRF pages for cases of COVID-19 that occur in the trial, which are expected outcomes of the trial. Therefore, COVID-19 and its complications/sequelae as well as all symptoms listed in Section 9.2.1.4 will not be reported according to the standard expedited process for SAEs, even though the event may meet the criteria for an SAE. However please note that all fatal cases resulting from COVID-19 and its complications/sequelae and from all other events will be reported as SAEs and need to be reported to the CRO within 24 hours (see section Reporting of SAEs). An AE form should be completed for any symptoms not listed in Section 9.2.1.4.

Definition of an Adverse Event (AE)

Definition of an AE:

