10.5 AEs

An AE is any untoward medical occurrence in a subject which does not necessarily have to have a causal relationship with the investigational product. In this trial, confirmed non-fatal cases of COVID-19 and complications/sequelae are not considered as AEs as they are captured on the CRF pages for COVID-19 illness which are expected outcomes of the trial and are analyzed as efficacy endpoints. Only for any complications and sequelae of COVID-19 illness not mentioned on the COVID-19 summary form in the electronic Case Report Form (eCRF), an AE form needs to be completed.

In this trial, for Phase 2b subjects, information on solicited local and systemic AEs occurring within 7 days after each CVnCoV vaccination and on unsolicited AEs occurring within 28 days after each CVnCoV vaccination are collected.

For all Phase 2b and Phase 3 subjects, information on medically attended AEs up to 6 months after second CVnCoV vaccination and SAEs, AESIs and AEs leading to vaccine withdrawal or trial discontinuation after the second CVnCoV vaccination to EOT Visit are recorded.

No other AEs require recording in the CRF.

The recording of AEs remains unchanged, irrespective of the subject rolling over to the OL-phase or not.

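### The symptom exemption from expedited SAE reporting is not tied to confirmed COVID-19, which leaves a gap for serious, non-fatal events not recognised as vaccine reactions or other AESIs

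*Protocol*

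**What the plan says.** Protocol 9.3.3 treats COVID-19 as an efficacy outcome that is documented on its own eCRF pages and not as an AE. It then states that "COVID-19 illness and its complications/sequelae as well as all symptoms listed in Section 9.2.1.4 will not be reported according to the standard expedited process", and adds that this applies even where the event would count as serious. Fatal events are carved back in and must be reported as SAEs.

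Appendix 10 repeats the exemption and closes with a companion sentence: "An AE form should be completed for any symptoms not listed in Section 9.2.1.4".

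Section 9.2.1.4, to which both point, defines a case for the blinded phase. A case is "defined as a positive SARS-CoV-2 specific RT-PCR test in a person with clinically symptomatic disease consisting of 1 or more of the following symptoms".

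Two other statements of the exclusion are narrower. Appendix 10, in its list of events that are not AEs, names only non-fatal COVID-19 cases and their complications. SAP 10.5 says "confirmed non-fatal cases of COVID-19 and complications/sequelae are not considered as AEs".

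Other protocol rules bear on the same events:
- Section 9.3.3.1 collects, in Phase 2b, "solicited systemic AEs (fever, headache, fatigue, chills, myalgia, arthralgia, nausea/vomiting and diarrhea").
- The Appendix 9 AESI list includes anosmia/ageusia, ARDS, serious local or systemic reactions after immunisation, and "Enhanced disease following immunization". Appendices 1 and 10 put AESIs on the same 24-hour timeline as SAEs.
- Appendix 10 makes every SUSAR expedited.
- Section 5.5.1 bars dose 2 after "Any SAE considered as related to the trial vaccine".

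**The concern.** The exemption is written by symptom, and nothing in either sentence links the symptom to a positive test. The listed symptoms are also those a vaccine is expected to cause. The protocol knows this: in 9.2.1.3.1, symptom messaging is held back until 4 days after each dose so that vaccine reactions are not taken for COVID-19. The SAE clause has no comparable safeguard.

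A site that applies the sentence as written could leave out of the SAE process a subject hospitalised with, say, high fever or vomiting, without confirmed COVID-19. SAEs and AESIs are primary safety endpoints, and related SAEs and SUSARs are among the events the DSMB follows under 5.5.2. Version 4.0 makes safety monitoring the main remaining purpose of the trial, and 9.3.3 carries the COVID-19 reporting procedure unchanged into the open-label phase.

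**Working it through.** No power, alpha or event figure is involved. The check compares texts, makes two simple counts, and traces the reporting routes.

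**1. What the clause adds.** The exemption names two items: (a) COVID-19 with its complications and sequelae, and (b) all symptoms on the 9.2.1.4 list. Symptoms of a confirmed case already fall under (a). So (b) is either redundant or it reaches symptoms outside a confirmed case. The Appendix 10 companion sentence favours the wider reading, because it sorts AE forms by whether the symptom is on the list and not by whether COVID-19 was confirmed.

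**2. Scope of each statement.**

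| Place | What is excluded | Tied to a COVID-19 case? |
|---|---|---|
| Protocol 9.3.3 | COVID-19, complications, all listed symptoms | Not for the symptoms |
| Appendix 10, opening paragraph | Same | Not for the symptoms |
| Appendix 10, events that are not AEs | Non-fatal COVID-19 cases and complications | Yes |
| SAP 10.5 | Confirmed non-fatal cases and complications | Yes |

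The first two rows are wider than the last two.

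**3. Overlap with expected reactions.** Of the 8 solicited systemic reactions in 9.3.3.1, fever, chills, headache, fatigue, myalgia (muscle or body aches), nausea/vomiting and diarrhoea are on the 9.2.1.4 list; arthralgia is not. That is 7 of 8 (7/8 = 87.5%).

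**4. Routes for a serious, non-fatal event with a listed symptom and no confirmed COVID-19.**
- *SAE*: withheld on the literal reading.
- *AESI*: open, on SAE timelines, if the investigator recognises a serious vaccine reaction or another listed condition. SAP 10.5.5 takes AESIs as the investigator recorded them, with no programmed search.
- *SUSAR*: open. The sponsor may also judge causality, but only on what sites send.
- *Medically-attended AE*: open through 6 months after dose 2, but not expedited.
- *Solicited diary*: Phase 2b only. Phase 3 is 32,500 of the 36,500 planned subjects (32,500/36,500 = 89%) and has none.

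The event that can slip through is therefore one that is serious, non-fatal, not confirmed as COVID-19, and not recognised as a vaccine reaction or other AESI.

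**5. Events on both sides.** Loss of taste or smell is an exempt symptom, while anosmia/ageusia is an AESI due within 24 hours. ARDS is an AESI and can also be a complication of COVID-19. No text says which instruction prevails.

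**The case against.** The strongest reply is that the clause should be read in context. Its paragraph is about COVID-19 as an endpoint, Appendix 10 introduces the exemption as a consequence of that, and the section it cites is the definition of a confirmed case. Other text treats listed symptoms as ordinary AEs:
- Section 9.3.3.1 records them as solicited AEs and has the systemic ones assessed for causality.
- Section 9.3.3.2 drops a visit with a negative test from medically-attended status only if there was no diagnosis and no prescribed medication.
- SAP 12.7.1.3 counts solicited AEs among the SAEs.
- Appendix 10 prefers a diagnosis to a symptom as the recorded term, so an admission with dyspnoea would normally be reported under its cause.

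This shows that the narrow meaning was probably intended. It does not make the operative sentences say so, and those are what a site follows.

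A reader might go further and infer that serious vaccine reactions resembling COVID-19 symptoms escape expedited reporting altogether, and that the dose-2 rule and DSMB review are thereby disabled. The documents do not support that. A recognised serious reaction is an AESI on SAE timelines; SUSARs and deaths are still reported. Section 5.5.1 turns on whether an SAE is judged related, and the clause limits a reporting process while accepting that the event may still be serious. The DSMB separately monitors COVID-19 cases by vaccine group for disease enhancement. Nor is all recording of COVID-19 complications barred: 9.3.3 asks for an AE form for those not on the COVID-19 summary form.

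**Conclusion.** The exemption is over-broad as worded in two places, and it disagrees with Appendix 10's own AE definition, with the AESI list and with SAP 10.5. The consequence is a limited gap: serious, non-fatal, listed-symptom events that are neither confirmed COVID-19 nor recognised as a vaccine reaction or other AESI can be missed by expedited reporting and by the DSMB's review of such reports. This weakens safety capture at one point; the other safeguards remain.

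The 7 of 8 and the 89% describe how far the wording reaches and how few subjects have a diary. They are not estimates of missed events, and the documents allow no such estimate. The conclusion assumes that at least some sites apply the sentence literally. The COVID-19 summary form is not among the documents, so what it would capture for an unconfirmed case is unknown. Trial vaccination precedes the version 4.0 follow-up, so the scenario shortly after a dose mainly concerns data already collected.

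**What to change.** 1. In 9.3.3 and Appendix 10, limit the symptom clause to listed symptoms that occur as part of a confirmed COVID-19 case recorded on the COVID-19 eCRF pages. State that listed symptoms outside such a case follow the ordinary AE/SAE rules, and bring the companion sentence in Appendix 10 into line.
2. Define a confirmed case by phase: RT-PCR-confirmed in the blinded phase; in the open-label phase, a case reported under that phase's procedure, including positive tests done outside the site. A condition of RT-PCR alone would not fit, because SAP 10.7.1.2 provides no RT-PCR confirmation of outside tests once version 4.0 is approved.
3. Check whether serious listed-symptom events without confirmation were left out of the data already collected. Illness visits with a negative RT-PCR are one place to start.
4. Reconcile 9.3.3 and Appendix 10 with the Appendix 9 list and the AESI timelines in Appendices 1 and 10, so that it is clear which instruction prevails for events on both sides, such as anosmia/ageusia and ARDS. This is a request to settle the rule. Sending every Appendix 9 event during COVID-19 through AESI reporting would make a case-defining symptom reportable within 24 hours, which is open to debate.

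The cost is a wording change in two places, a site memo, the retrospective check, and some additional SAE forms, a few of them reclassified later when COVID-19 is confirmed.
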